5.2 Cycle Definition

In the absence of a delay due to toxicity, each treatment cycle lasts 28 days with a \pm 3 day window during Induction and 28 days with a \pm 7 day window during Maintenance.

During the Induction phase (Cycles 1-6), Day 1 of each cycle is defined as the first day of administration of ublituximab.

During the Maintenance phase (Cycles 7-25), ublituximab is administered every 2 cycles (every 8 weeks) starting on Day 1 of Cycle 8, and each cycle is defined as 28 days.

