7.0 DOSE DELAY / MODIFICATION GUIDELINES

7.1 Dose Delays/ Modification

- Toxicities will be graded using the NCI CTCAE v 5.0.
- Baseline values are from the last values obtained prior to treatment.
- Both acalabrutinib and umbralisib may be dose reduced for toxicity. If a toxicity occurs, both drugs (as well as ublituximab) may be interrupted until resolution to Grade 1, to baseline, or as noted in Table 7.1.1. Following that, either or both oral agents may be dose reduced based on suspected attribution. General guidelines for recommended dose delays and modifications are provided below.
- No reduction in the dose of ublituximab is permitted. If Grade 4 anaphylaxis is observed at any point during ublituximab treatment, permanently discontinue ublituximab treatment and intervene as per investigator discretion.
- All study drugs may be delayed for a maximum of 8 weeks to allow recovery of toxicities as specified in the tables below.
- If one of the study drugs is discontinued for toxicity, patient may continue therapy with the other study drugs.
- When treatment interruption is required for toxicity, all drugs are held. If ublituximab is suspected to be the primary reason for a recurrent toxic event, it may be discontinued only in consultation with the Study PI.

Table 7.1.1 Recommended Dose Modifications

NCI-CTCAE Grade	Dose Delay and/or Modification
Hematologic Adverse Event	
Neutropenia	
Grade \leq 2 neutropenia	Provide supportive care as warranted. Maintain current dose and schedule of acalabrutinib. Maintain current dose of umbralisib. If applicable, maintain full dose and schedule of ublituximab.
Grade 3 neutropenia	Provide supportive care as warranted. Maintain current dose and schedule of acalabrutinib. Maintain current dose of umbralisib. For recurrent or persistent Grade 3 neutropenia unresponsive to maximum supportive care:

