Correlative tumor tissue ^v	X ⁿ										X ^o					
Bone marrow biopsy/ aspirate ^{p, v}	X										X					

- a. Screening activities to occur within 28 days prior to start of protocol therapy except for laboratory assessments.
- b. In the absence of treatment delay, each treatment cycle lasts 28 ± 3 days during Induction, and 28 ± 7 days during Maintenance.
- c. Maintenance phase for participants with stable disease or better response (PR or CR) at the end of Induction therapy.
- d. Activities to be performed within 72 hours prior to study drug administration.
- e. The Safety 30 days post-last dose assessments to occur 30 (± 7) days post-last dose or, if > 30 days elapsed since last dose, within 7 days after decision to end treatment. Expedited reporting will occur during this period. Safety follow-up may be extended until resolution/ stabilization of reportable AEs.
- f. For participants yet to progress, Active Follow-up will occur at 6, 12, 18 and 24 months (± 30 days for all) from last on-treatment scan until disease progression or the initiation of a new anti-lymphoma therapy.
- g. Participants who end Active Follow-up will enter Survival Follow-up. Survival assessment to occur bi-annually or as requested by the Study PI via medical record review, review of social security registry, or telephone call.
- h. *Standard physical exam* includes weight.
- i. *Vital signs*: heart rate, blood pressure, respiration rate, and temperature.
- j. *Women of childbearing potential*: Pregnancy serum test. For the screening time point, serum pregnancy test must be performed within 3 days prior to start of protocol therapy.
- k. *Screening laboratory assessments* to be performed within 14 days prior to start of protocol therapy.
- l. *Serum chemistry panel* to include: glucose, Blood Urea Nitrogen (BUN), creatinine, uric acid, total protein, albumin, magnesium, bicarbonate, calcium, inorganic phosphorous, sodium, potassium, chloride, total bilirubin, alkaline phosphatase, ALT, AST, and LDH.
- m. Correlative blood will also be collected at time of relapse. Refer to [Section 9.1.3](#) for additional information.

- n. Archival tumor tissue to be submitted post-enrollment when available. Refer to [Section 9.1.1](#).
- o. If safe and feasible, submission of left-over tissue from a standard of care tumor biopsy (fresh core or excisional biopsy) for participants who progress/relapse during study is encouraged. Refer to [Section 9.1.1](#).

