- p. Bone marrow biopsies will be performed at the following time points if feasible (please contact Study PI if bone marrow collection is not feasible at either time point to receive a waiver):
 - 1- At baseline** (during screening). If a patient had a recent bone marrow biopsy (within 90 days), this time point may be omitted after a discussion with the Study PI. In this case, a correlative sample will not be submitted.
 - 2- At the time a CR is suspected** based on imaging results (within 8 weeks after such result).
 - 3- At the time of disease relapse.**
- At each time point, bone marrow samples will be collected for correlative studies ([Section 9.1.2](#)).
- q. Every other cycle starting on C8D1 (i.e. on days of ublituximab infusion).
- r. Ublituximab infusions are on Day 1 of C8, C10, C12, C14, C16, C18, C20, C22, C24, C26, C28, and C30.
- s. Disease assessments (imaging) to occur on Days 1 (\pm 7 days).
- t. PET-CT is strongly preferred. CT in lieu of PET-CT is allowed if patient is in CR and CR was already confirmed by PET-CT, and for patients for whom PET-CT is not feasible (with Study PI's approval).
- u. Every 6 months (+/- 2 weeks) from last on treatment scan until end of protocol therapy.
- v. NGS panel (HopeSeq at City of Hope), FISH analysis, conventional cytogenetics and IHC should be performed on tumor diagnostic material (lymph node, bone marrow, peripheral blood) based on disease characteristics, per institutional practice standards at screening. Every effort should be made to collect such data ([Section 9.3](#)).
- w. Serum virology to include HBsAg, HBc antibody, HCV antibody and CMV IgG and IgM (or may do CMV by PCR at investigator discretion). If HBc antibody, HCV antibody or CMV IgG or IgM is positive, subject must be evaluated for the presence of active HBV, HCV or CMV by PCR.
- x. CMV screening by PCR for all subjects receiving study treatment beginning in Cycle 4 and approximately every 3 to 4 cycles thereafter aligned with study visits.
- y. This time point serves as TLS assessment. TLS assessment will be performed on Day 2 (+ 1 day).
- z. Activities to be performed on D15 +/- 3 days.

* EOM = End of maintenance. Visit to occur at the end of Cycle 25 (with a +7 days window) and to include disease assessment (imaging).

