12.0 STATISTICAL CONSIDERATIONS

12.1 Study Design

This is a multicenter, single-arm Phase 2 study evaluating AU2 therapy for patients with previously untreated MCL. Patients will first receive 6 cycles of AU2 (acalabrutinib + umbralisib + ublituximab) induction; those who achieve SD or better response after induction will then receive 19 cycles of maintenance with the 3 agents, during which ublituximab will only be given every 2 cycles. Each cycle will be 28 days. Participants may continue therapy with acalabrutinib beyond 25 cycles of Induction + Maintenance therapy at the treating physician's discretion. Response will be evaluated just prior to C4, C7 (End of Induction), C14, C20 , EOM (end of maintenance), every 6 months thereafter until end of protocol therapy (if patient continues with oral agents only beyond 25 cycles), and at Safety visit.

The primary endpoint is complete response (CR) rate after AU2 induction therapy. Secondary endpoints include toxicities of AU2 induction and maintenance therapy, overall response rate to protocol therapy, duration of response, progression free survival, and overall survival.

The study sample size is based on the desire to discriminate a promising CR rate of 50% (alternative hypothesis) from a disappointing CR rate of 25% (null hypothesis) after AU2 induction. These response rates were chosen because 1) BR, a current standard, has been associated with an ORR of 80-90% and a CR rate of 40% [5, 7]; 2) In the phase 2 ACE-LY-004 trial in R/R MCL, treatment with acalabrutinib was associated with an ORR of 81% and a CR rate of 40% [39]. However, it is anticipated that this study will enroll a higher proportion of patients with high-risk MCL (*TP53* aberrations, CK) where BR is ineffective.

Simon's optimal two-stage design will be used. In the first stage, 9 evaluable patients will be accrued. If there are 2 or fewer CRs in these 9 patients, the study will be stopped. Otherwise, 15 additional evaluable patients will be accrued for a total of 24. The null hypothesis will be rejected and AU2 induction therapy will be considered promising if 10 or more CRs are observed in 24 evaluable patients. This design yields a 1-sided type I error rate of 0.05 and power of 0.8. When the CR rate is disappointing (25%), there is an 60% chance that the study will be terminated after the first stage.

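### Maintenance scans are tied to cycle numbers, so a toxicity hold that moves Day 1 moves the scan and tends to date progression later in held patients; the effect is modest and cheap to remove

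*Combined protocol and SAP*

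**What the plan says.** Study Calendar, footnote s: "Disease assessments (imaging) to occur on Days 1", with a 7-day window either side. The staging columns name C4D1, C7D1, C14D1 and C20D1. The last on-treatment scan in the 25-cycle programme belongs to the EOM visit: "Visit to occur at the end of Cycle 25 (with a +7 days window".

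Section 12.1 uses the same anchors: "Response will be evaluated just prior to C4, C7 (End of Induction), C14, C20", then EOM.

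Cycle length is conditional. Section 5.2: "In the absence of a delay due to toxicity, each treatment cycle lasts 28 days with a" 3-day window in Induction and a 7-day window in Maintenance. Calendar footnote b repeats the condition: "In the absence of treatment delay, each treatment cycle lasts" 28 days within those windows. Section 5.2 ties Day 1 to the ublituximab dose in Induction, but for Maintenance it defines each cycle simply as 28 days.

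Section 7.1: "All study drugs may be delayed for a maximum of 8 weeks to allow recovery of toxicities".

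Only after EOM does imaging run on time: every 6 months during continued acalabrutinib (footnote u), and at 6, 12, 18 and 24 months in Active Follow-up (footnote f). Both count from the last on-treatment scan; footnote f reads "from last on-treatment scan until disease progression or the initiation of a new anti-lymphoma therapy". A slip during treatment therefore carries forward.

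Section 11.3 defines PFS and DOR without a rule for dating progression or handling late scans. Section 12.5 estimates PFS by plain Kaplan-Meier.

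**The concern.** Progression found by imaging is dated no earlier than the scan that shows it. If the scan waits for the next cycle, a patient whose drugs are held is imaged later than one who is not, and the delay is linked to toxicity. No passage keeps an on-treatment scan on its calendar date during a hold, and the analysis has no step that would correct for it. There is no control arm to share the distortion, and the protocol cites BR's median PFS as background (Section 2.1.2.1).

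There is also a consistency problem. One site may read the Maintenance cycle as elastic and another as a fixed 28 days, and so schedule the same patient's scan weeks apart. The elastic reading is the natural one: C14 and C20 are both ublituximab cycles in Section 5.3, so sites will tend to book the scan around the infusion.

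**Working it through.** **The plan's own figure.** The only stated design calculation is the Simon design (stop at 2 or fewer CRs in 9; promising at 10 or more in 24; 25% against 50%). It reproduces: exact alpha 0.0485, power 0.805, early stopping 0.601 under the null, against the stated 0.05, 0.8 and 60%. It uses no scan after C7D1. Nothing is stated for PFS or DOR, so the rest is a new calculation.

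**Scan dates.** With 28-day cycles, scans fall on days 84, 168, 364, 532 and 700 (weeks 12, 24, 52, 76, 100). C7D1 to C14D1 is 7 × 28 = 196 days, or 28 weeks. The 7-day cycle window, always used in one direction, moves this by 7 × 7 = 49 days, giving 21 to 35 weeks. One 8-week hold before C14 gives 196 + 56 = 252 days and moves the later scans to days 420, 588 and 756.

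**Model.** Exponential PFS with median 35.4 months × 30.4375 = 1,077.5 days, so S(t) = 2^(−t/1077.5). Progression is dated at the next scheduled scan, so recorded PFS at time t equals S at the last scan on or before t. Values: S(168) = 89.8%, S(364) = 79.1%, S(532) = 71.0%, S(700) = 63.7%. True 24-month PFS is 62.5%.

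**Assumed, not in the documents:** 25% or 50% of patients have one hold; it starts uniformly over days 168-700, lasts 4-8 weeks (mean 42 days) and moves every later scan. Of these holds, 196/532 = 36.8% precede C14, 168/532 = 31.6% fall between C14 and C20, and 31.6% follow C20.

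**At the usual landmarks**
- 12 months (day 365, one day after C14D1): holds before C14 change the record from S(364) to S(168), +10.6 points. 10.6 × 0.368 = 3.9; × 0.25 and × 0.50 gives +1.0 and +2.0.
- 18 months (day 548, 16 days after C20D1): holds between C14 and C20 give 79.1 − 71.0 = +8.1; holds before C14 give S(406) − S(532) = 77.0 − 71.0 = +6.0. 0.316 × 8.1 + 0.368 × 6.0 = 4.8; this gives +1.2 and +2.4.
- 24 months (day 730, 30 days after EOM): the same steps, counting only holds longer than about 30 days as crossing the landmark, give +1.3 and +2.7.

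Simulation gives the same 18- and 24-month figures. Across medians of 24 to 48 months the excess at those two landmarks is about 1 to 3 points.

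**Between scans**, a held patient's later scan has already taken place and has caught later progressions as well:
- 14-17 months: S(406) − S(364) = −2.1; × 0.368 × 0.25 or 0.50 gives −0.2 or −0.4.
- 20-22 months: S(574) − S(532) = 69.1 − 71.0 = −1.9; × 0.684 × 0.25 or 0.50 gives −0.3 or −0.65.
- 25-28 months: S(742) − S(700) = 62.0 − 63.7 = −1.7; × 0.25 or 0.50 gives −0.4 or −0.8.

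**Whole-curve summaries (simulation).** Restricted mean PFS rises by about 0.7-1.4 days. The recorded median is about 41 months with no holds, unchanged with 25% held, and about 37 with 50% held, against a true 35.4; it jumps because it must fall on a scan date.

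**Dating lag.** For true progression on days 168-700, mean lag is about 92 days with no hold and about 105 in held patients; about 56% of held patients are dated later and 8% earlier. A single maximal 8-week hold adds about 15-22 days.

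**Precision.** SE at 24 patients = √(0.637 × 0.363 / 24) = 0.098. The 24-month excess is 1.3/9.8 to 2.7/9.8, or 0.13 to 0.28 SE.

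**The case against.** A reader might infer that every dose delay postpones the scan and that PFS and DOR are therefore overstated. The documents do not support either step.

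- **Not every hold counts.** Section 5.2's plain 28-day definition for Maintenance can be read as a fixed calendar. Section 7.1 says that an interruption for toxicity holds all drugs, yet rows of Table 7.1.1 delay one drug while another continues, for example Grade 1-2 pneumonitis. A daily oral drug can also stop and restart within a cycle. Such holds need not move Day 1. The passages need reconciling; this point takes no position on which should govern treatment.
- **The direction is not uniform.** The usual landmarks fall just after nominal scans, which is why a hold pushes events across them. Between scans the sign reverses, and the median can fall. A 2-week hold before C14 in all patients gives 63.2% at 24 months, against 63.7% with none.
- **The existing lag dominates.** Scan gaps of 24-28 weeks already build in about 91 days of mean lag.
- **Mitigation exists.** The calendar lets assessments become more frequent as clinically indicated, and Section 11.1 permits extra restaging. Deaths are dated independently of scans. All of this shrinks the modelled effect, but none of it is required during a hold.
- **DOR can be offset** when first response is itself first seen at a delayed scan. Responses first seen at C4 or C7 get no such offset from Maintenance holds.
- **Consequence.** PFS and DOR are secondary and descriptive, with no threshold and no planned comparison with BR.

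All of this stands and limits the claim. What remains is that scan timing depends on toxicity and on how a site reads Section 5.2.

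**Conclusion.** The point holds in a limited form. Through EOM, Maintenance staging follows cycle numbers, so a hold that moves Day 1 moves the scan, and progression tends to be dated later in held patients. Under the stated assumptions the distortion is about 1-3 points upward at 12, 18 and 24 months, slightly downward between scans, and about a day in restricted mean. It is small beside a standard error of about 10 points, and the primary CR endpoint and the Simon decision do not depend on it. The size rests on hold frequency, length and timing that the documents do not give, and on a model without deaths or unscheduled scans. A general claim that PFS and DOR are overstated is not established. This is a worthwhile low-cost improvement, not a threat to the trial's main conclusion.

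**What to change.** Keep C4D1 and C7D1 tied to cycles, because the primary endpoint is CR after six cycles. In the calendar, footnote s, the EOM note and Section 12.1, schedule the later on-treatment scans at weeks 52, 76 and 100 from C1D1, with a window of 2 weeks either side, regardless of cycle number or treatment delay. These are the present nominal days 364, 532 and 700, so no scan is added. This also settles the Section 5.2 ambiguity as far as imaging is concerned.

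Cost: wording changes, and some scans will not coincide with a dosing visit; in a delayed patient the week-100 scan will precede the EOM visit. The change does not remove the ordinary lag from 24-28 week gaps, and a landmark close to a scan date will stay sensitive to the window. A stated rule for dating progression and an interval-censored sensitivity analysis of PFS would complement it.

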11.0 ENDPOINT DEFINITIONS/MEASUREMENT OF EFFECT

11.1 Assessment of Response

Lymphoma response/progression will be evaluated using 2014 Lugano Classification (see [Appendix C](#)). [51]

Disease assessment will be performed by PET-CT. In patients in whom PET-CT is not feasible, CTs may be used in place of a PET-CT after discussion with the Study PI ([name]). Patients must have a bone marrow biopsy performed at baseline and to confirm CR (if suspected based on imaging). After CR, additional bone marrow biopsy is only required if clinically indicated and at relapse. Additional necessary restaging studies including dedicated CT scans or MRI, are permitted at the investigator's discretion. PET-CT and CT results will be read by a radiologist at each study site and investigator response assessment will be performed.

For patients with progression of disease on imaging, it is strongly recommended that a confirmatory biopsy be obtained whenever possible.

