11.2 Primary Endpoint(s)

Complete response (CR) rate: defined as the proportion of response-evaluable participants (see [Section 12.2](#)) that achieve a CR at the end of induction therapy. If a patient achieves CR earlier during induction therapy but is PD at the end of induction, the patient will be considered end of induction non-CR. If a patient achieves a CR earlier during induction but does not have a response evaluation at the end of induction for some reason (for example early termination of induction due to patient refusal), the prior CR will be carried over as the end of induction CR.

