APPENDIX C: LYMPHOMA RESPONSE CRITERIA [54]

Response	Site	CT-Based Response	PET-CT Based Response
Complete Response	Lymph nodes and extralymphatic sites	Complete radiologic response (all of the following) 
 Target nodes/nodal masses must regress to ≤ 1.5 cm in longest diameter (LD_i). No extralymphatic sites of disease. 	Complete metabolic response (even with a persistent mass) 
 Score $\leq 3^*$ with or without a residual mass on 5-point scale[†]. It is recognized that in Waldeyer's ring or extranodal sites with high physiologic uptake or with activation within spleen or marrow (e.g., with chemotherapy or myeloid colony-stimulating factors), uptake may be greater than normal mediastinum and/or liver. In this circumstance, complete metabolic response may be inferred if uptake at sites of initial involvement is no greater than surrounding normal tissue even if the tissue has high physiologic uptake.
	Nonmeasured lesion	Absent	Not applicable
	Organ enlargement	Regress to normal	Not applicable
	New lesions	None	None
	Bone marrow	Normal by morphology; if indeterminate, IHC negative	No evidence of FDG-avid disease in marrow
		Partial remission (all of the following)	Partial metabolic response
Partial Response	Lymph nodes and extralymphatic sites	
 $\geq 50\%$ decrease in SPD of up to 6 target measurable nodes and extranodal sites When a lesion is too small to measure on CT, assign 5 mm X 5 mm as the default value When no longer visible, 0 X 0 mm For a node > 5 mm X 5 mm, but smaller than normal, use actual measurement for calculation 	
 Score 4 or 5[†] with reduced uptake compared with baseline and residual mass(es) of any size At interim, these findings suggest responding disease At end of treatment, these findings indicate residual disease
	Nonmeasured lesion	Absent/normal, regressed, but no increase	Not applicable
	Organ enlargement	Spleen must have regressed by $> 50\%$ in length beyond normal	Not applicable
	New lesions	None	None

Response	Site	CT-Based Response	PET-CT Based Response

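### The Study Calendar lets a patient in PET-confirmed CR have CT alone at the primary-endpoint scan, Appendix C defines CR differently for CT, and Section 11.2 does not say how that scan is scored

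*Combined protocol and SAP*

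**What the plan says.** Induction imaging falls at C4D1 and C7D1 (Study Calendar), and Section 12.1 identifies the C7 assessment as the end of induction. The documents give three conditions for using CT instead of PET-CT:

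- Section 10.0, footnote t, which covers the whole imaging row: "CT in lieu of PET-CT is allowed if patient is in CR and CR was already confirmed by PET-CT". It also allows CT where PET-CT is not feasible, with Study PI approval, and it strongly prefers PET-CT.
- Section 11.1: "In patients in whom PET-CT is not feasible, CTs may be used in place of a PET-CT", after discussion with the Study PI. There is no exemption for patients already in CR.
- Study Schema, note 1: PET/CT preferred, or CT with the Study PI's approval. The note states no infeasibility condition, although it refers the reader to the Study Calendar and Section 11.1.

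Appendix C has separate columns for the two modalities. The PET-CT column defines CR as "Complete metabolic response (even with a persistent mass") and treats organ enlargement as not applicable. The CT column says "Target nodes/nodal masses must regress to" 1.5 cm or less, and enlarged organs must return to normal.

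Section 11.2 counts CR at the end of induction and settles two cases after an earlier CR. The first begins "If a patient achieves CR earlier during induction therapy but is PD at the end of induction" and is scored non-CR. In the second, there is no end-of-induction evaluation and the earlier CR is carried over.

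**The concern.** The patients whom footnote t moves to CT are the early complete responders, and they can be moved at the visit that decides the primary endpoint. Consider a patient in metabolic CR at C4D1 with an inactive 2.0 cm node that does not change. By PET-CT at C7D1 this patient is a CR. By the CT column the node is too large for CR. The result is PR if the sum of products of diameters (SPD) has fallen by at least 50%, and SD if it has fallen by less. Neither is PD and the patient has been evaluated, so neither of the two cases in Section 11.2 applies and the general definition is all that remains.

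Error in the opposite direction is also possible. CT cannot show renewed FDG uptake in a normal-sized node, so a patient who would no longer be a CR by PET could be kept as one.

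Either way, the recorded endpoint can depend on which scan was ordered. Scans are read at each of four sites with investigator assessment, so sites could resolve the question differently. Accrual stops at 2 or fewer CRs of 9, and success needs 10 of 24. A single reclassified patient can change either decision.

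**Working it through.** **Step 1. Reproduce the design.** Inputs from Section 12.1: the aim is to "discriminate a promising CR rate of 50% (alternative hypothesis) from a disappointing CR rate of 25% (null hypothesis"); the stage 1 rule is "If there are 2 or fewer CRs in these 9 patients, the study will be stopped"; success is 10 or more CRs in 24; and "This design yields a 1-sided type I error rate of 0.05 and power of 0.8".

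The probability of declaring success at a scored CR rate p is the sum over x = 3 to 9 of P(X1 = x) × P(X2 ≥ 10 − x), with X1 ~ Bin(9, p) and X2 ~ Bin(15, p).

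- p = 0.25: 0.0485 (type I error). P(X1 ≤ 2) = 0.6007, matching the stated 60%.
- p = 0.50: 0.8055 (power). P(X1 ≤ 2) = 0.090.

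The stated operating characteristics are correct. A search over two-stage designs also returns 2/9 and 9/24 as the optimal boundaries.

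**Step 2. Model the literal reading.** Let f be the share of true end-of-induction CRs scored non-CR because of modality:

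f = e × u × g, and scored rate = 0.50 × (1 − f)

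- e = share of CRs already reached by C4D1
- u = share of those given CT alone at C7D1
- g = share of those with a residual target node over 1.5 cm

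The documents give none of the three. All are assumptions: e = 0.5; u = 10%, 25% or 100%; g = 10%, 20% or 30%. For example, u = 100% and g = 20% give f = 0.5 × 1 × 0.2 = 0.10 and a scored rate of 0.50 × 0.90 = 0.45.

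| CT use at C7D1 (u) | f at g = 10 / 20 / 30% | Scored CR rate | Power |
|---|---|---|---|
| 0% | 0 | 0.500 | 0.806 |
| 10% | 0.005 / 0.010 / 0.015 | 0.4975 / 0.4950 / 0.4925 | 0.799 / 0.793 / 0.786 |
| 25% | 0.0125 / 0.025 / 0.0375 | 0.4938 / 0.4875 / 0.4813 | 0.790 / 0.773 / 0.755 |
| 100% | 0.05 / 0.10 / 0.15 | 0.475 / 0.450 / 0.425 | 0.737 / 0.656 / 0.566 |

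In the 100% row, the chance of stopping at stage 1 when the true rate is 50% rises from 0.090 to 0.117, 0.150 and 0.188.

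**Step 3. Effect on type I error.** Applying the same f values from the 100% row to the null rate of 0.25 lowers type I error from 0.0485 to 0.035, 0.025 and 0.017. Losses of this kind count against the regimen. Missed FDG recurrence acts the other way, by raising the scored rate. The documents give no basis for sizing it, so it is not modelled.

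**The case against.** The strongest reply is that nothing in the documents requires a PET-confirmed CR to be re-scored from scratch against the CT column. PD is the only finding that Section 11.2 names as cancelling an earlier CR. Footnote t speaks of a patient who is in CR, which can be read as CT follow-up of a response already established, and the response is investigator-assessed. This stands. A reader might infer that such patients are certain to become PR and non-CR, but the documents do not settle that. Non-CR follows from the general definition, and from the carry-over being written for patients with no evaluation. The opposite inference can be drawn from naming PD alone. What is established is that the rule is missing. The PR label is not fixed either, because a smaller SPD decrease gives SD.

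The second reply is that the affected group is narrow. A patient must be in PET CR at C4D1, receive CT at C7D1 despite the stated strong preference for PET-CT, and keep a node over 1.5 cm or an enlarged organ. Patients enrolled on marrow involvement alone may have no target node. This also stands. A reader might take the 100% row as the expected loss, but it assumes that every early complete responder gets CT, and the documents do not support that. At 10% to 25% CT use, the loss is about 1 to 5 percentage points of power.

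The third reply is that Section 11.1 already requires PET-CT where feasible. It does, but a site following footnote t would also be following the protocol. A preference does not override the permission given in the same footnote.

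**Conclusion.** The point holds as a conflict between footnote t, Section 11.1 and Schema note 1 that reaches the primary-endpoint scan, together with a missing scoring rule for CT after a PET-confirmed CR. Because Appendix C's CR criteria differ by modality, the same disease state can be CR or non-CR depending on the scan ordered and on how the site fills the gap.

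The size cannot be determined from the documents. Under the assumptions in the table, the effect runs from less than 1 point of power (0.806 to 0.799) to about 24 points (0.806 to 0.566), and it depends mainly on how often CT is used at C7D1. The figures apply only if the literal reading is followed; if investigators keep the CR, that loss does not arise. The modelled direction lowers type I error, so by itself it cannot make a false claim of activity more likely. Missed FDG recurrence could, and its size is unknown.

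The sample size and stated error rates need no change. This should be corrected because it concerns how the primary endpoint is measured and costs little to put right.

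**What to change.** 1. In footnote t, limit the exemption for patients already in PET-confirmed CR to scans after C7D1. The C7D1 scan is then PET-CT unless PET-CT is not feasible, which is what Section 11.1 already says.
2. Reconcile footnote t, Section 11.1 and Schema note 1 so that all three state the same condition for CT. Editing the footnote alone would leave the Schema wording different.
3. Add one sentence to Section 11.2: where the C7D1 scan is still done by CT after a PET-confirmed CR, the CR is retained unless an Appendix C progression criterion is met.

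The cost is PET-CT rather than CT at one visit for early complete responders, a scan the protocol already strongly prefers. The Section 11.2 sentence adds no procedure. It would still leave FDG recurrence undetected in the few patients scanned by CT, which is why the first change matters more. Sample size, visit schedule and decision rule are unchanged.
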